5.5.4 Follow-Up Inferential Analysis- Concomitant Vaccination Analysis	17
5.5.5 Adjustments to Primary and Follow-Up Analyses	17
5.5.6 Attributable Risk (AR) Estimation	19
6. Medical Record Review	19
7. Ethical Evaluation	19
8. Quality Assurance and Control	19
9. References	20
10. Appendix.....	23
10.1 Concomitant Vaccination Code List	23
10.2 Immunocompromised algorithm.....	25

1. Background/Introduction

There were approximately 290,000-650,000 influenza-related hospitalizations and 19,000-58,000 influenza-related deaths in the United States (U.S.) during the 2022-2023 influenza season (October 1, 2022- April 30, 2023).⁽¹⁾ Evidence from previous influenza seasons, shows that persons aged 65 years and older are at an increased risk for more severe influenza-related symptoms and complications due to age-related comorbidities and decline in immune function.⁽²⁾ Approximately 50-70% of influenza-related hospitalizations and 70-85% of influenza-related deaths during the 2010-2011 and 2019-2020 influenza seasons were among individuals 65 years of age and older.⁽²⁾ Vaccination continues to be the primary tool for influenza prevention.⁽³⁾ Influenza vaccines are recommended for anyone 6 months of age and older and are typically developed with new formulations each influenza season to target the four most prevalent influenza viruses based on available data.⁽³⁾ Safety monitoring of annual influenza vaccines, particularly among persons 65 and older, is useful because these vaccines are reformulated each year and given this is a particularly vulnerable population.

Historically, adverse events (AEs) following influenza vaccination have been rare. Previous studies conducted in the U.S. and globally over the course of various influenza seasons largely support the safety profile of influenza vaccines showing no elevation in risk associated with several AEs following influenza vaccination.⁽⁴⁻⁹⁾ However, other studies have found associations between influenza vaccines and certain AEs including anaphylaxis, encephalitis or encephalomyelitis, Guillain Barré -Syndrome (GBS) and transverse myelitis.⁽¹⁰⁻¹⁶⁾ For some AEs, observed elevations in risks have largely been attributed to influenza infection.^(4, 17) There is also a potential for the risk of these AEs to be impacted by concomitant vaccination; evidence shows that vaccines such as COVID-19, hepatitis B, pneumococcal, tetanus, diphtheria, pertussis (Tdap), and Shingrix vaccines have displayed an association with some of these AEs when administered independently or concomitantly with other vaccines.⁽¹⁸⁻²¹⁾

For the 2022-23 season, there are multiple influenza vaccines available: Afluria Quadrivalent, Fluarix Quadrivalent, FluLaval Quadrivalent, Fluzone Quadrivalent, Flucelvax Quadrivalent, Flublok Quadrivalent, Fluzone High-Dose Quadrivalent, Fluad Quadrivalent, and FluMist Quadrivalent.⁽²²⁾ Of these vaccines, three are preferentially recommended by the Centers for Disease Control and Prevention (CDC) for use in people aged 65 years or older: Fluzone High-Dose Quadrivalent inactivated vaccine, Flublok Quadrivalent recombinant vaccine, and Fluad Quadrivalent adjuvanted vaccine.⁽³⁾

This document details the specifications for a self-controlled case series (SCCS) study in the U.S. to assess the incidence of select AEs (anaphylaxis, encephalitis or encephalomyelitis, GBS, and transverse myelitis) following administration of influenza vaccines approved for use during the 2022-2023 influenza season. These AEs were chosen because they have been studied in other vaccines. This study will be implemented in the Centers for Medicare & Medicaid (CMS) Medicare claims database among persons aged 65 years and older.

2. Objectives

The objective of this public health study is to assess the safety profile of influenza vaccines administered during the 2022-2023 influenza season in the U.S. population aged 65 years and older. The specific objectives are outlined below.

- **Primary Objective:** To estimate the incidence rate of the following AEs: anaphylaxis, encephalitis or encephalomyelitis (including acute disseminated encephalomyelitis (ADEM)), GBS, and transverse myelitis after exposure to influenza vaccines in the risk interval, compared to the incidence rate of the AEs in the control interval. Assessment of AEs incidence rates will be performed for all influenza vaccine types combined together (overall), and for high-dose and adjuvanted vaccine groups separately. Vaccine groupings are presented in Table 3.
 - **Follow-Up Objective (if applicable):** If there is a statistically significant association in the primary analysis indicating a potentially increased rate of an AE in the risk compared to control interval, we will evaluate the potential contribution of concomitant (same-day) vaccination with at least one of five other vaccines to the elevated incidence rate for the given AE. The analysis for the specific outcome(s) with a statistically significant result will be stratified by concomitant vaccination status (influenza vaccination alone, and influenza vaccine *with any* same-day concomitant vaccination). Where sufficiently powered, follow-up analyses by combinations of concomitant vaccines may be performed.
 - Concomitant vaccines of interest are listed below.^{1(23, 24)} Table E1 can be referenced for associated vaccine code lists:
 - COVID-19 Bivalent (Pfizer-BioNTech, Moderna)
 - Pneumococcal (PCV15/20, PPSV23)
 - Hepatitis B
 - Tetanus (Tdap, tetanus, diphtheria (Td))
 - Shingrix

3. Data Sources

The study will be performed using the Medicare administrative claims database. The Medicare claims database includes well-defined longitudinal data that captures healthcare service utilization for millions of enrollees across multiple care settings including inpatient, outpatient-emergency department (OP-ED) and outpatient non-ED, professional services non-laboratory and laboratory, and pharmacy settings.

The Medicare Study will include CMS Medicare Shared System Data (SSD) to capture longitudinal healthcare information for persons aged 65 years and older in the study population. Medicare Fee-for-Service (FFS) Part A (inpatient) and Part B (outpatient and physician services) will be used to capture patient's vaccination history, healthcare services, health-related covariates, and diagnoses. Medicare

¹The selection of concomitant vaccines is based on vaccines recommended for administration in the population aged 65 years and older.

Part D data will also be used as a supplementary source to capture patient’s vaccination history. The CMS Medicare Enrollment Database (EDB) will be used to capture patient’s demographic characteristics. Medicare claims data undergo three stages of processing: enumeration, adjudication, and final payment. This study will use CMS Medicare SSD which consists of claims sourced after enumeration to reduce data lag. Information on nursing home residency status will be captured from The Minimum Data Set (MDS) 3.0, a mandatory clinical assessment administered to all residents in Medicare and Medicaid certified nursing homes.⁽²⁵⁾ Table 1 summarizes data characteristics for the Medicare claims data source.

Table 1. Description of Medicare Claims Data Characteristics

Data Source	Claims Type	Update frequency	Data Lag*	Population Enrolled
CMS Medicare Fee-For-Service Shared Systems Fee-for-Service Data (SSD)	Pre-Adjudicated	Daily	>80% data completeness in 30-70 days for inpatient claims	>34 million beneficiaries annually

*Data lag is based on 2020 claims delay distribution

4. Exposure and Adverse Events

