5.1. Study Population

The study will include eligible vaccinees enrolled in Medicare during the study period who receive an influenza vaccine and meet the inclusion and exclusion criteria below, regardless of AE occurrence. All eligible vaccinees will be used to estimate attributable risks (ARs), whereas a subset population with an observed AE occurrence during the observation period (case population) will be used to estimate IRRs.

Inclusion criteria

- (i) Beneficiaries must be enrolled in Medicare Part A (inpatient insurance) and Part B (outpatient and physician services insurance) FFS plans during the observation period, which extends from vaccination date through the earlier of the AE control period end, or any of the censorship criteria (i.e., disenrollment, subsequent influenza vaccination, study period end, or death). Definitions for the risk, control and observation period can be referenced in Section 5.4.
 - If a follow-up concomitant vaccines analysis is applicable, Part D insurance will also be required during the observation period to ensure comprehensive capture of concomitant vaccinations.
- (ii) Beneficiaries must have received an influenza vaccine during the study period and prior to the vaccination cutoff date (latest date vaccine administration will be eligible for inclusion in the study). Further information on the rationale for this cutoff is provided in Section 5.5.1.
- (iii) Beneficiaries will be required to have continuous enrollment in Medicare Parts A and B FFS from 365 days prior to influenza vaccination through the earlier of the observation period end, or any of the censorship criteria (i.e., disenrollment, subsequent influenza vaccination, or death).

- (iv) For the case population only, each case must have a record of an incident AE diagnosis during the observation period.

Exclusion criteria

- (i) Medicare beneficiaries less than 65 years of age at the time of influenza vaccination.
- (ii) Individuals that do not contribute *any* follow-up time to both risk and control intervals i.e. beneficiaries that meet any of the censorship criteria during the risk interval prior to accumulating time in the control interval will be excluded.
- (iii) Individuals vaccinated with multiple influenza vaccine brands on the same day or multiple influenza vaccinations (same/different brand) within 3 days of each other.
- (iv) People who received a diagnosis of the AE during the AE-specific clean period.

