5.5.2 Descriptive Analysis

Descriptive analyses will be performed for the primary and follow-up analyses. For each of the case populations, the descriptive analyses will summarize the cases (counts and percentages) and unadjusted outcome rates following influenza vaccination by risk and control intervals. Descriptive statistics will be summarized for influenza vaccines overall and by high-dose and adjuvanted vaccine groups. Statistics will be summarized overall and by the following characteristics.

- (i) Demographics: Age, sex, race/ethnicity, dual eligibility status, region³, urban/rural, area deprivation index (ADI)⁽³¹⁾, nursing home residency status
- (ii) Health status: Influenza diagnosis (defined by the ICD-10-CM code J10.X) in the 30 days prior to influenza vaccination
- (iii) Concomitant vaccines administered on the influenza vaccine administration date (as specified in Section 2)
- (iv) Baseline health characteristics (defined by ICD-10 codes) in the 183 days prior to influenza vaccination:
 - Prior hospitalization
 - Asthma
 - Blood disorders
 - Chronic lung disease
 - Diabetes
 - Heart disease
 - Kidney disorders
 - Liver disorders
 - Neurological or neurodevelopmental conditions
 - Malignant neoplasms
 - Immunocompromised status (as binary covariate)⁴⁽³²⁾
 - Charlson comorbidity index

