5.5.4 Follow-Up Inferential Analysis- Concomitant Vaccination Analysis

5.5.4.1 Incidence Rate Ratio (IRR) Estimation

The follow-up inferential analysis will only be performed for AEs for which a statistically significant elevated incidence rate ratio is observed from the primary analysis. This analysis will be implemented consistently with the primary analysis specified in Section 5.5.3.1, except the analysis will be conducted in two separate subgroups. One subgroup will include persons with an observed influenza vaccination *with any* concomitant (same-day) vaccination, and the other subgroup will include persons with influenza vaccination *without any* concomitant (same-day) vaccination. Where sufficiently powered, follow-up analyses may be performed by combinations of concomitant vaccines.

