5.5.5 Adjustments to Primary and Follow-Up Analyses

5.5.5.1 Seasonality Adjustment Analysis

Both the primary and follow-up analyses specified in Section 5.5.3 and 5.5.4 will include a seasonality adjustment, given that certain AEs included in the study demonstrate seasonal patterns in incident rates. This seasonality adjustment will adjust for changes in the baseline rate of AEs during different calendar months in the year. The baseline rate of AEs will be estimated from a similar population during the same calendar months in previous years, and subsequently included as an offset term in the regression model. For each AE, 2021 will be the comparator year used to adjust for changes in the baseline rate. Both 2020 and 2021 were considered as historical years for the seasonality adjustment; 2021 was selected as the adjustment period given that 2021 rates are more recent and thus likely more reflective of rates during the study period, and since the 2020 period has the potential to underestimate events due to changes in healthcare utilization during the early pandemic.⁽³³⁾

The Farrington and seasonality-adjusted model that will be used for the main primary and follow-up analyses is defined below.⁽²⁷⁾

$$\log(E(Y|X)) = \beta_1 * risk_interval + \log(w(t)) + \log(seasonal_risk) + strata(patient_id)$$

$$Y = AE$$

risk_interval = binary term indicating AE occurrence in risk interval

w(t) = Farrington adjusted weight

$$seasonal_risk = \frac{1}{IR_r * t} \sum_{m=1}^{12} (IR_m * t_m)$$

IR_m = daily incident rate for month *m*

IR_r = daily incident rate for reference month *r*

t_m = number of days in an interval in month *m*

$$t = \text{number of days in an interval or equivalently } t = \sum_{m=1}^{12} t_m$$

patient_id = term identifying the patient

In this model, the null and alternative hypotheses can be written as, respectively:

$$H_0: e^{\beta_1} = 1 \quad H_a: e^{\beta_1} \neq 1$$

Where e^{β_1} is the IRR for the AE in the risk interval compared to control interval adjusting for seasonality and curtailed observation time. A statistically significant coefficient at a pre-specified alpha level of 0.05 will indicate a statistically significant association between influenza vaccination and the AE.

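### Listed vaccines given on days other than the influenza vaccination date are an unhandled time-varying exposure, and their recipients are analysed as having had influenza vaccine alone

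*Protocol*

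**What the plan says.** Section 1 of the protocol names COVID-19, hepatitis B, pneumococcal, Tdap and Shingrix among vaccines that "have displayed an association with some of these AEs when administered independently or concomitantly with other vaccines".

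Every later use of these vaccines is restricted to the day of influenza vaccination:

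- **Section 2, Follow-Up Objective:** "we will evaluate the potential contribution of concomitant (same-day) vaccination with at least one of five other vaccines". The comparison is "stratified by concomitant vaccination status (influenza vaccination alone, and influenza vaccine" with any same-day listed vaccine.
- **Section 5.5.4.1:** the model is that of the primary analysis, "except the analysis will be conducted in two separate subgroups", split by same-day status.
- **Section 5.5.2:** the descriptive tables cover "Concomitant vaccines administered on the influenza vaccine administration date".

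The rules that could deal with a second vaccine concern influenza vaccines only. In Section 5.1 follow-up ends at "any of the censorship criteria (i.e., disenrollment, subsequent influenza vaccination, study period end, or death", and the multiple-vaccine exclusion covers several influenza brands on one day or "multiple influenza vaccinations (same/different brand) within 3 days of each other". The model in Section 5.5.5.1 has one exposure term, "risk_interval = binary term indicating AE occurrence in risk interval", plus the Farrington weight and the seasonal offset.

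**The concern.** A self-controlled design removes confounders that stay fixed within a person. Another vaccine on another day is not fixed. If it has its own risk window, that window falls partly or wholly in the influenza risk interval or in the control interval, depending on when the dose was given. The seasonal offset uses 2021 population rates by calendar month and cannot correct for one person's vaccine timing in 2022-23.

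Two results are exposed:

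- **The follow-up analysis** asks whether co-vaccination contributes to a raised rate. Someone given Shingrix seven days before the influenza vaccine is analysed as having had influenza vaccine alone. A raised IRR in that stratum could then be read as an effect of the influenza vaccine by itself.
- **The primary IRR** carries the same unmodelled exposure. Upward bias could create a signal. Downward bias could keep a real one from reaching significance, and the follow-up analysis, which runs only after a significantly raised primary IRR, would then never start.

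**Working it through.** The protocol gives no frequency, timing or effect size for other-day doses, so there is no figure of its own to reproduce. The check below is expected-value arithmetic on the protocol's intervals.

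**Inputs from the protocol (Table 4).** For GBS, encephalitis or encephalomyelitis, and transverse myelitis: risk days 1-42 (R = 42) and control days 43-90 (C = 48). For anaphylaxis: risk days 0-1 (R = 2) and control days 3-16 (C = 14).

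**Assumed inputs.** A share g of the analysed group has a listed vaccine on day x. That vaccine multiplies the event rate by φ in its own window, days x+1 to x+42. The true influenza IRR is 1 and follow-up is complete. The Farrington and seasonal adjustments are set aside.

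**Formula.** Let a and b be the days of that window falling in the risk and control intervals, averaged over x. Then

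expected IRR = [1 + g(φ−1)a/R] / [1 + g(φ−1)b/C].

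**Average overlaps**

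- Doses on days −28 to −1: a = 42 + x, running from 14 to 41, mean 27.5; b = 0.
- Doses on days 1 to 28: a = 42 − x, mean 27.5; b = x, mean 14.5.
- Doses on days 29 to 60: a totals 91 over 32 days, mean 2.84. b totals 497 (days 29-42) + 252 (days 43-48) + 426 (days 49-60) = 1175, mean 36.72.

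**Results at g = 20%, φ = 2**

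- Before: 1 + 0.2 × 27.5/42 = 1.13.
- Days 1-28 after: 1.131 / (1 + 0.2 × 14.5/48) = 1.131/1.060 = 1.07.
- Days 29-60 after: (1 + 0.2 × 2.84/42) / (1 + 0.2 × 36.72/48) = 1.0135/1.1530 = 0.88. A true IRR of 1.5 becomes 1.5 × 0.879 = 1.32.

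| Assumed g, φ | 28 days before | Days 1-28 after | Days 29-60 after |
|---|---|---|---|
| 10%, 1.5 | 1.03 | 1.02 | 0.97 |
| 20%, 2 | 1.13 | 1.07 | 0.88 |
| 30%, 2 | 1.20 | 1.10 | 0.83 |

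**Where the direction changes.** For a dose on day x from 1 to 42, the bias is zero when (42 − x)/42 = x/48, that is x = 2016/90 = 22.4. Earlier doses inflate the IRR and later ones deflate it.

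**Even spread.** Over days −41 to 89, excluding day 0 (130 days), a averages 1722/130 = 13.25 and b averages 2016/130 = 15.51. At g = 20%, φ = 2 the result is 1.0631/1.0646 = 0.999, so the biases nearly cancel.

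**Anaphylaxis**, assuming g = 10%, φ = 5 and a window of 0-1 days from the dose. A dose on day −1 or +1 gives 1 + 0.4 × 1/2 = 1.20. A dose on days 3-15 gives 1/(1 + 0.4 × 2/14) = 0.946. A dose on day −2 or earlier has no effect.

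**Benchmark.** Section 5.5.1 discusses one bias in numbers, claims delay, at (1/0.9) − 1 = 11%.

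**The case against.** **The scope is stated openly.** Same-day is used consistently, and Section 5.5.4.1 describes the comparator as having no same-day vaccine. That stands: this is a design weakness and not a contradiction. It does not remove the point, because Section 2 calls that comparator influenza vaccination alone while Section 1 allows the other vaccines a risk of their own. An unseen analysis plan may hold sensitivity analyses, but the strata, the censoring rules and the model equation are fixed in this document.

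**The size is assumed.** This stands too. Section 1 speaks of some of the outcomes, whereas the check applies one effect and one 42-day window to every listed vaccine. The milder case, 0.97 to 1.03, is smaller than the claims-delay bias that the protocol accepts.

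**Stronger readings a reader might infer, which the protocol does not support:**

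- *That misplaced people bias both strata.* The strata are fitted separately and within person, so people in the alone stratum cannot bias the other IRR. The with-any stratum is affected only by people who have a same-day dose and also another listed dose on a different day.
- *That the same-day definition biases the primary IRR.* The primary model does not use co-vaccination status. Its exposure to bias comes from having no term, exclusion or censoring for other vaccines.
- *That later doses always mask a signal.* They do so only from about day 23.
- *That the follow-up question becomes unanswerable.* Partial contamination blurs the contrast but does not abolish it.

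**A careless remedy can do equal harm.** Suppose the alone stratum required no listed vaccine through the end of observation, and an event deters later vaccination. Assume 20% vaccinated evenly over days 1-90, full deterrence after the event, and no effect of either vaccine. Retention is 1 − 0.2 × 21.5/90 = 0.952 for risk-interval cases and 1 − 0.2 × 66.5/90 = 0.852 for control-interval cases, giving a spurious IRR of 0.952/0.852 = 1.12. This stands, and it limits the fix to classification on doses up to day 0.

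**Conclusion.** The concern holds as a correctable design weakness. Other-day doses of vaccines that the protocol itself regards as possible causes are neither modelled, excluded nor censored, and people whose only listed doses fall on other days enter the alone stratum. The alone-stratum IRR, the contrast between strata and the primary IRR can therefore be biased.

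Under the assumed inputs in the table, with doses concentrated in one timing band, the estimate ranges from 0.83 to 1.20 when the truth is 1. At the upper end this exceeds the 11% claims-delay figure, and for evenly spread doses it is close to nil. Share, effect and timing are not in the protocol, so neither the size nor the direction is known. That is a reason to measure it, not evidence that the results will be wrong.

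**What to change.** 1. **Follow-up strata.** Define the alone stratum as no listed vaccine from day −42 through day 0 (day −1 through day 0 for anaphylaxis). Put people with an earlier other-day dose and no same-day dose in a separate category. Do not classify on doses after influenza vaccination, since an event may deter them.
2. **Sensitivity model.** For the primary and follow-up analyses, prespecify a version of the conditional Poisson model with a time-varying indicator for each other-day dose's own risk window (1-42 days; 0-1 days for anaphylaxis), pooled across the listed vaccines if events are sparse. State the caution that later doses may depend on the event, which touches assumption (i) in Section 5.2.
3. **Description.** Tabulate other-day listed doses by timing relative to influenza vaccination, so that the inputs assumed here can be replaced by data.

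**Cost.** The codes are in Table E1 and the claims are already held. There will be fewer cases in the alone stratum and some loss of precision. COVID-19, pneumococcal and hepatitis B doses are captured through Part B. Shingrix and tetanus capture will be incomplete before vaccination and in the primary population, because Section 5.1 requires Part D only for the follow-up analysis and only during observation. Requiring Part D for the look-back days as well would close that gap for the follow-up analysis, at the price of a smaller population.
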